4.4 Per-protocol sample

The per-protocol sample will be limited to subjects who will be randomized and treated in compliance with the protocol. Only observations or specimens collected according to the protocol will be included in the analyses using the per-protocol population. If a subject will receive one or more treatments out of compliance with the protocol schedule, any observations or specimens collected after the out-of-compliance treatment will be excluded from the analyses using the per-protocol population.

The overall timing associated with the study is based on our previous clinical study experience. Approximately 50 patients per year receive skull surgery that requires 1 hour or more of drilling time at Washington University School of Medicine (WU). We estimate to finish the study within 4 years. If subject enrollment numbers are consistently below expectations as determined by the study team and DSMB, plans will be made to add additional sites or adjust study inclusion criteria (e.g. including head/skull surgeries requiring less than 1 hour of drilling time).

Serious feasibility or design difficulties: If one year after the start of the trial, < 50% of the planned accrual goals are met, DSMB and the study team will discuss difficulties in recruitment. Patient remuneration will be revised, if needed. If there are not enough patients meeting inclusion/exclusion criteria, then the criteria will be revised without impacting study objectives. If there are not enough patients that undergo more than 1-hr drilling time during surgery, we will explore including into the study, patients with drilling time at least 45 minutes, expanding audiometric criteria, or expanding to different institutions.

5 GENERAL ASPECTS FOR STATISTICAL ANALYSES

5.1 General Methods

- All analyses and summaries will be produced using SAS® version 9.4 (or higher).
- Standard descriptive statistics will be used to describe distribution of demographic, clinical, and audiometric characteristics as well as outcome measures for all the study samples listed in section 4. For continuous level characteristics Q-Q plots and Shapiro-Wilk test will be used to test assumption of normality. If continuous level data is found to be normally distributed data, mean and standard deviation will be used as descriptive statistics, and if the assumption of normality is violated, we will report median and range for description of these variables. Frequency and relative frequency will be used for description of categorical level variables.
- The same number of decimal places as in the raw data will be presented when reporting range, 1 more decimal place than in the raw data will be presented when reporting the mean and median, and 2 more decimal places than in the raw data will be presented when reporting the standard deviation.
- Unless stated otherwise, tabular summaries will present columns for the active treatment arm ("ZNS pre-op" and "ZNS post-op"), placebo arm, and overall.
- Unless stated otherwise, the relative frequency will be based on the number of non-missing observations. The column header will still contain the number of subjects in the treatment group. There will be a row for the number of non-missing observations in the table (at each time point, if required) for each variable being summarized.
- Any calculated p-values will be presented to 3 decimal places; p-values less than 0.001 will be presented as 'p<0.001' and p-values greater than 0.999 will be presented as 'p>0.999'.
- All relevant subjects data will be included in listings and sorted by treatment group, subject ID, and visit, as applicable, for all randomized subjects.
- Unscheduled or repeat assessments will not be included in summary tables unless specified. All assessments will be included in the subject listings.
- All tables, listings and figures will include footers that identify the name of the program that created the output, together with the date and time on which it was created. Headers will include the total number of pages that the presentation contains and, for each page, the number of the page within the presentation.

5.2 Missing Data

Every attempt will be made to ensure data completeness. We do not anticipate much loss to follow-up because of the relatively short time follow-up interval. Conservatively, we would estimate that fewer than 5% of subjects will drop out/withdraw from the study. The subject will be withdrawn from the study follow-up and procedures if the subject withdraws consent, or the sponsor decides to close the study.

Data loss, if any, would almost likely be due to subjects refusing to complete or not returning at all for the post-surgery assessment of PTS 30 days (+/- 3 days). If the subject reschedules the post-surgery appointment for a later date for any reason, and if this delay is within 30 days of the

scheduled date, the data will be considered valid and used in the efficacy analysis. Any measure outside this time window of +30 days will be defined and considered as missing data.

Missing PTS at 30 days will be imputed using SAS PROC MI procedure within each treatment group using the distribution implied by the non-missing data for the specific treatment group. The SAS code below using Multiple Imputation by Chained Equations (MICE) via the Fully Conditional Specification (FCS) statement will be used to impute the missing data under the missing at random (MAR) assumption.

```
PROC MI DATA=X SEED=<value> NIMPUTE=10 OUT=MI_OUT1 NOPRINT;
CLASS GROUP;
VAR AGE PTA LSurg......;
FCS LOGISTIC(PTS);
RUN:
```

Each of the 10 complete data sets will be then analyzed using Fisher's exact test. One-sided p-value (p_i) from Fisher's exact test will be converted to a z-value using the inverse Normal transformation [1,2], i.e. $z_i = \Phi^{(-1)}(1-p_i)$, where $\Phi^{(-1)}(\cdot)$ represents the inverse standard Normal cumulative distribution function.

SAS funtion to convert Fisher's exact P-value to Z-value is as follows:

```
Z_i= QUANTILE('NORMAL', p_i, 0, 1);
```

The estimated z-vales from the 10 imputed datasets will be then combined following Rubin's rules using PROC MIANALYZE procedure in SAS which will be of the form:

```
PROC MIANALYZE DATA=Y;

MODELEFFECTS Z_i;

STDERR Z_i;

ODS OUTPUT ParameterEstimates=XX;

RUN:
```

The pooled estimate of z-vales from PROC MIANALYZE procedure will be then converted to probability value using the following SAS function:

```
P value=PROBNORM(estimate);
```

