7.1.1 Analysis of primary outcome variable

Efficacy analysis at the end of the study

The primary outcome measure for assessing effectiveness of ZNS (100 mg PO) either pre-op or post-op compared to the placebo group will be the proportion of subjects defined as PTS positive 30 days (+/-3 days) after surgery.

Audiogram will be performed to look for PTS. Patients for whom the difference at any frequency from 2-6 kHz in hearing thresholds (30 days (\pm -3 days) post-surgery - Baseline) is \geq 10 dB HL will be defined as PTS positive. Primary analysis and sensitivity analyses will be carried out on the primary endpoint.

Primary analysis

Frequency and relative frequency will be used to describe the distribution of the primary outcome measure in each study group. To assess efficacy, Fisher's exact test will be used to compare the proportion of subjects with PTS positive in ZNS group with the proportion of patients with PTS positive in the placebo group.

The confidence intervals will be calculated using method 10 described by Newcombe RG, 1998 and also described by Altman et al.

 Altman, Douglas, et al., eds. Statistics with confidence: confidence intervals and statistical guidelines. https://www.amazon.com/Statistics-Confidence-Intervals-Statistical-Guidelines/dp/0727913751

Let n_1 be the number of participants in placebo group, and r_1 the number of participants with PTS in the placebo group. $p_1=r_1/n_1$ be the proportion of PTS in the placebo group, and $q_1=r_2/n_2$ the proportion of participants that do not have PTS in placebo group.

 l_1 and u_1 are the lower and upper limits of the $100(1\text{-}\alpha)\%$ confidence interval for p_1

Using Wilson method we calculate:

$$A_1 = 2r_1 + z^2$$

$$B_1 = z\sqrt{z^2 + 4r_1q_1}$$

$$C_1 = 2(n_1 + z^2)$$

$$l_1 = \frac{(A_1 - B_1)}{c_1}$$
 $u_1 = \frac{(A_1 + B_1)}{c_1}$

 z_a = the 100(1 – α)th percentile of the standard Normal distribution.

Let n_2 be the number of participants in ZNS group, and r_2 the number of participants with PTS in the ZNS group. $p_2=r_2/n_2$ be the proportion of PTS in the ZNS group, and q_2 the proportion of participants that do not have PTS in ZNS group.

l₂ and u₂ are the lower and upper limits of the 100(1-α)% confidence interval for p₂

$$A_2 = 2r_2 + z^2$$

$$B_2 = z\sqrt{z^2 + 4r_2q_2}$$

$$C_2 = 2(n_2 + z^2)$$

$$l_2 = \frac{({\rm A}_2 - {\rm B}_2)}{c_2} \qquad \qquad u_2 = \frac{({\rm A}_2 + {\rm B}_2)}{c_2}$$

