 z_a = the $100(1-\alpha)^{th}$ percentile of the standard Normal distribution.

The proportion difference between groups is: $\mathbf{D} = \mathbf{p_1} - \mathbf{p_2}$

The lower (l_D) and the upper limits (u_D)of 100 (1- α)% confidence interval for D will be calculated as:

$$l_D = D - \sqrt{(p_1 - l_1)^2 + (u_2 - p_2)^2}$$

$$u_D = D + \sqrt{(p_2 - l_2)^2 + (u_1 - p_1)^2}$$

A supportive logistic regression analysis will be done with covariates: age, pre-op hearing dichotomized to normal to minimal hearing loss and slight to mild loss, noise exposure history dichotomized to high risk and low risk, exposure categorized as low (8-hour equivalent A-weighted sound level in decibel (LAeq8hr) < 80 dBA), moderate (LAeq8hr > 80 dBA but < 90 dBA), or high (LAeq8hr > 90 dBA).

```
PROC LOGISTIC DATA=X;
CLASS GROUP;
   MODEL PTS = COVARIATE1 COVARIATE2.. ;/*Covariates are as mentioned above*/
RUN;
```

Sensitivity analysis of the primary endpoint

The potential impact of missing primary endpoint data will be explored in sensitivity analyses using multiple imputation. Two sensitivity analyses performed:

Sensitivity 1: MI analysis under the missing not at random assumption (MNAR) Sensitivity 2: Logistic regression tipping point analysis under the assumption of data missing at random.

Sensitivity 1

Proc MI procedure in SAS will be used to impute missing data for study treatment groups using the distribution implied by the non-missing patient data within the placebo group. The SAS code to impute data for Sensitivity analysis 1 under the MNAR assumption will be of the form:

```
PROC MI DATA=X SEED=<value> NIMPUTE=10 OUT=MI_OUT1 NOPRINT;
CLASS GROUP;
VAR AGE PTA LSurg......;
FCS LOGISTIC(PTS);
RUN;
```

Post imputation each of the imputed 10 datasets will be analyzed using the same approach as for the primary outcome measure. The estimates of the analysis of the 10 imputed datasets will be then combined following Rubin's rules using PROC MIANALYZE procedure in SAS which will be of the form:

```
PROC MIANALYZE PARMS=GMPARMS COVB=GMCOVB PARMINFO=GMPINFO WCOV BCOV

TCOV; / *dataset "gmparms" contains the estimates and associated standard errors
for the mean parameters from each of the M=10 imputed data sets.
dataset "gmcovb" contains the asymptotic covariance matrics
dataset "gmpinfo" contains parameter info*/

MODELEFFECTS INTERCEPT AGE PTA LSurg......;
RUN;
```

Sensitivity 2

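### SAP 5.2 names Rubin's rules for pooling the imputed Fisher tests, but its p-value leaves out the between-imputation variance, and text and code give z opposite signs

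*SAP*

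**What the plan says.** - **Primary test.** SAP 7.1.1 says Fisher's "exact test will be used to compare the proportion of subjects with PTS positive in ZNS group" with placebo. Its primary-analysis paragraph does not mention imputation. The ITT sample (SAP 4.2) is everyone randomized.
- **Missing outcomes.** SAP 5.2 imputes missing 30-day PTS ten times and applies Fisher's test to each completed data set. It converts each one-sided p to z and says "The estimated z-vales from the 10 imputed datasets will be then combined following Rubin's rules using PROC MIANALYZE procedure".
- **Sign of z.** The text of SAP 5.2 defines z as the inverse normal of 1 − p, as SAP 9 does for the interim analysis. The SAS line is "Z_i= QUANTILE('NORMAL', p_i, 0, 1", the inverse normal of p.
- **Pooling code.** MIANALYZE receives `Z_i` both as the effect and as its own standard error (`STDERR Z_i`). SAP 5.2 then says "The pooled estimate of z-vales from PROC MIANALYZE procedure will be then converted to probability value using the following SAS function", and the line that follows begins "P value=PROBNORM(estimate".
- **Sensitivity 1** (SAP 7.1.1, and the same in Protocol 12.2.1): "Post imputation each of the imputed 10 datasets will be analyzed using the same approach as for the primary outcome measure". The pooling statement is then "MODELEFFECTS INTERCEPT AGE PTA LSurg".
- **Protocol 12.2.2, Missing Data** has the same imputation step but pools `group`, without saying which analysis that term comes from.
- **Expected missingness** (SAP 5.2): "Conservatively, we would estimate that fewer than 5% of subjects will drop out/withdraw from the study".

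**The concern.** Rubin's rules exist to add the uncertainty due to imputation to the variance of the pooled estimate. Here the pooled z is referred to a standard normal as if nothing had been imputed. Relative to the method named, the error has one direction: a favourable result looks stronger than it should.

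A programmer who notices this cannot fall back on MIANALYZE's own test, because the standard error supplied is wrong. A programmer who follows the text for z and the code for p gets 1 − p. In Sensitivity 1, Fisher's test yields no intercept, age or PTA coefficient to pool, and no treatment term is listed.

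As soon as one 30-day audiogram is missing, SAP 5.2 is the only written route to a pooled Fisher p-value for the primary endpoint.

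**Working it through.** **Inputs from the plan.** 78 per arm, PTS 50% on placebo and 25% on ZNS, one-sided alpha 0.0125, stated power 80.4% (SAP 2.7); ten imputations and under 5% missing (SAP 5.2).

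**The plan's own figure.** The arcsine approximation for Fisher's test is Φ(√(2n)·|asin√(p₁ − 1/2n) − asin√(p₂ + 1/2n)| − 2.2414). With n = 78, p₁ = 0.50, p₂ = 0.25 it gives 80.41%, matching the stated 80.4%. Full enumeration gives power 80.7% and, at 50% v 50%, a rejection rate of 0.00997.

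**Sign.** At p = 0.0125 the text gives z = +2.2414 and the code −2.2414. PROBNORM returns 0.0125 from the code's z and 0.9875 from the text's. The code alone is self-consistent.

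**Variance.** With each z given variance 1 and m = 10, Rubin's total variance is T = 1 + 1.1B. The test is mean z/√T on a t distribution with df = 9(1 + 1/(1.1B))². The SAP uses mean z with variance 1. Taking B = 0.05, about the simulated mean at 5% missing:
- T = 1.055 and df is about 3,311.
- Reaching p = 0.0125 needs a pooled z of 2.303, not 2.241.
- A pooled z of 2.30 gives 0.0107 as written and 0.0126 with Rubin.

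**Why MIANALYZE's own test is no fallback.** With `STDERR Z_i` the within-imputation variance is mean(z²). Then T = mean(z²) + 1.1B ≥ (mean z)², so |t| cannot exceed 1. With the code's sign, the supplied standard error is also negative when ZNS is favoured.

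**Worked examples.** These assume four missing per arm, imputation within arm from Beta(x + 0.5, n − x + 0.5) posteriors and no covariates. The first is deliberately borderline.

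| Observed PTS, ZNS v placebo | Observed-data p | Median p as written | Median p, Rubin |
|---|---|---|---|
| 23/74 v 37/74 | 0.0146 | 0.0122 | 0.0144 |
| 22/74 v 37/74 | 0.0092 | 0.0076 | 0.0091 |
| 21/74 v 37/74 | 0.0056 | 0.0045 | 0.0056 |

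In the first row p is at or below 0.0125 in 53% of imputation seeds as written and 24% with Rubin.

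**Simulated trials.** Same imputation model, data missing completely at random; 800,000 trials per rate under 25% v 50%.

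| Missing | Power as written | Power, Rubin | Verdict differs |
|---|---|---|---|
| 1% | 80.5% | 80.2% | 0.3% |
| 3% | 80.3% | 79.2% | 1.1% |
| 5% | 80.0% | 78.2% | 1.8% |

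Every difference is significant as written and not with Rubin.

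Under 50% v 50% (1,500,000 trials per rate):

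| Missing | Null rejection as written | Null rejection, Rubin |
|---|---|---|
| 5% | 0.0101 | 0.0085 |
| 10% | 0.0120 | 0.0087 |
| 11% | 0.0124 | 0.0087 |
| 12% | 0.0128 | 0.0087 |

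Rates of 5% and above lie outside the plan's expectation and are assumptions.

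**With a predictive covariate** in the imputation model (assumed: binary, 50% prevalence; 5% missing on average; missing completely at random or depending on the covariate), power is 80.0–80.2% v 78.3–78.8%. The verdict differs in 1.4–1.8% of trials, and null rejection is 0.0096–0.0097 v 0.0083–0.0085.

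**The case against.** The strongest reply is that no false-positive harm arises in the planned range. Fisher's test is conservative, and at up to 5% missing the as-written rule rejects a true null about as often as the complete-data test (0.0101 at 5%, against 0.00997). The p-value is too small relative to Rubin's, not relative to a breached error rate. Rubin pooling makes a conservative test more so and takes power just under 80% at 3% and 5% missing. Describing the method as a mean z, without naming Rubin's rules, would also end the contradiction. All of this is correct. However, the mean-z rule holds its level only because Fisher's test leaves slack, which is used up at about 12% missing, and it still carries no imputation uncertainty.

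The examples have 4 of 78 missing (5.1%), just beyond the plan's expectation, and in the two away from the boundary the median p falls on the same side of 0.0125 under both methods. That stands too.

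A reversed p-value near 0.99 would probably be noticed in the double programming and review of SAP 11.2. But two programmers who both follow SAP 5.2 would agree on a p-value without B, so that check does not catch the main error.

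The Sensitivity 1 code is offered as a template. It is still a template for a model, attached to a sentence that calls for Fisher's test.

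Finally, Protocol 6.0 defines the primary proportion over participants tested at 30 days, and SAP 5.1 bases relative frequencies on non-missing data unless stated otherwise. It is therefore not fully settled that the headline p is the pooled one. SAP 4.2 and 5.2 favour that reading; the doubt is a reason to state it.

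**Conclusion.** The concern holds. The p-value coded in SAP 5.2 is not the Rubin p-value its text names, and it errs towards ZNS whenever the pooled z favours ZNS and B > 0. The standard error given to MIANALYZE makes that procedure's own test unusable, and text and code disagree on the sign of z. Sensitivity 1 has no pooling step that works for Fisher's test.

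The practical effect at under 5% missing is small: at most about 1.8 power points and 1.8% of verdicts at the design effect, with type I error still below 0.0125. These sizes rest on the stated imputation models and missingness assumptions; the omission of B and the sign conflict rest on none. It should be corrected, but it does not threaten the trial's validity at the planned level of missing data.

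**What to change.** 1. **One sign.** Keep z as the inverse normal of 1 − p, in line with SAP 9, and code `Z_i = QUANTILE('NORMAL', 1-p_i, 0, 1)`.
2. **Standard error.** Add a variable `SE = 1`, the nominal standard error of a z-value, and write `STDERR SE`.
3. **p-value.** Compute `1 - PROBT(Estimate/StdErr, DF)` from MIANALYZE's pooled estimate, total standard error and degrees of freedom. If B = 0, DF is undefined; use `1 - PROBNORM(Estimate)`.
4. **Sensitivity 1** (SAP 7.1.1 and Protocol 12.2.1). Use the same pooling wherever Fisher's test is applied, in place of the listed coefficients. If the logistic model is meant, say so and name the treatment effect that is pooled.
5. **Primary analysis.** State in SAP 7.1.1 and in the Protocol that the primary Fisher test is pooled this way when PTS is missing.
6. **Protocol 12.2.2.** Have the sponsor state which analysis the pooled `group` term belongs to.

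The cost is a few lines of code and text. Favourable p-values become slightly larger when data are missing, which costs about 0.3, 1.1 and 1.8 power points at 1%, 3% and 5% missing.

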6 STUDY SUBJECTS

6.1 Disposition of Subjects

Subject disposition data will be summarized by treatment group and overall for the ITT Sample Set. The number randomised, treated, completed or discontinued from the study, including reasons for discontinuation as well as the number of subjects in each sample set and subject treatment status will be summarized descriptively.

All disposition data will be listed. Inclusion and exclusion criteria will also be listed.

6.2 Demographics Characteristics

Demographic characteristics will be summarized descriptively by treatment group for the Safety Sample Set, including:

- Age (years) at time of consent
- Sex
- Ethnicity
- Race

Demographics characteristics will be listed.

6.3 Medical History and Surgical History

Medical and surgical history will be coded with Medical Dictionary for Regulatory Activities (MedDRA) version 24.0 and summarized by System Organ Class (SOC), Preferred Term (PT), and by treatment group with counts and relative frequency based on the Safety Sample Set. A subject will only be counted once in an SOC and an SOC/PT combination.

All medical history data will be listed.

6.4 Concomitant Medications

Concomitant medications are defined as all medications (excluding study dose) taken on or after the date of first dose administration up to and including the date of the post operative Day 30 visit.

Medications that started before the date of first dose and are ongoing after the date of first dose will be considered as concomitant medications.

Medications will be coded using the Anatomical Therapeutic Chemical (ATC) classification codes and preferred drug name according to the World Health Organization (WHO) Drug Global B3, (March 2021). Summary table will be provided for concomitant medications for the Safety Sample Set, presenting the number and relative frequency of subjects by treatment group, and will be sorted in alphabetical order of ATC Level 2 and then PT in the overall column. For each subject, the medication will be counted only once within a given ATC level 2 and only once within a given preferred drug name level. A subject may appear more than once if she has more than one concomitant medication coded under different ATC categories.

Concomitant medications will be presented in a listing..

6.5 Treatment Administration

The number of doses taken will be summarized by treatment group and overall for the Safety Sample Set and include

- Number and percentage of subjects who received dose 1
- Number and percentage of subjects who received dose 2
- Number and percentage of subjects who received both doses

Dose administration information will be listed for all safety subjects.

6.6 Protocol Deviations

Protocol deviations will be summarized for the Safety Sample Set by type of deviation. Protocol deviations for all subjects who signed an informed consent will be entered into Pharm-Olam's Clinical Trial Management System. Examples of deviation types may include but are not limited to:

- Inclusion/exclusion criteria not met
- Informed consent
- Randomization
- Essential/Study Documents
- Investigational product administration and handling
- CRF/source data
- Sample/tests handling
- Equipment/Facilities
- Visit procedures
- Other

Protocol deviations will be reviewed by Washington University and Pharm-Olam medical and clinical (including statistical) personnel and classified as major or minor deviations at a blinded data review meeting prior to database lock.

Major protocol deviations are defined as those that may significantly impact the quality (i.e., completeness, accuracy, and reliability) or integrity of key trial data; or indicates systemic problem within the study or its conduct; or that might significantly impact the rights, safety or welfare or trial subjects.

Protocol deviations will be presented in each deviation category as a major or minor deviation by treatment group. The total count of protocol deviations within each treatment group will be used as the denominator for relative frequency in this table. All protocol deviations will be presented in a data listing.

